TITLE OF THE PROTOCOL: Medication monitoring in general practice: clinical impact of implementing a nurse-led Adverse Drug Reaction (ADRe) Profile in older adults with 5 or more prescribed medicines

Short title/Acronym: Medication monitoring in general practice/ADReGP

Chief Investigator **[name]**

Faculty **Faculty of Health and Life Sciences**

Date **20/11/2020**

SU Sponsor reference:	RIO 034-20
IRAS Number	292693
NHS REC reference:	21/WA/0042
Clinicaltrials.gov number:	NCT04663360

Sponsor: **Swansea University**
 Representative of the Sponsor:
 [name]
 Academic Lead for Research Integrity
 Research Engagement & Innovation Services
 Swansea University
 [name]
 [contact]
 Email: [contact]
 This is the SU authorised signatory

NHS R&D Trust Lead **1) Swansea Bay UHB: [name]**
 Swansea Bay University Health Board
 [name]
 Swansea University
 [name]
 [name]

Contact details
 [name] | [name]
[contact]

2) Hywel Dda UHB: [name]

Research & Development Manager (Study set-up & data)

Hywel Dda University Health Board

[name]

Withybush Hospital

[name]

[name]

Pembrokeshire

[name]

Contact details

Email / e-bost: [contact]

Tel / Rhiff ffôn: [name] or [name]

3) Cardiff and Vale UHB: TBC

STUDY SUMMARY/SYNOPSIS

TITLE	Medication monitoring in general practice: clinical impact of implementing a nurse-led Adverse Drug Reaction (ADRe) Profile in older adults with 5 or more prescribed medicines
SHORT TITLE/Acronym	Medication monitoring of older adults with polypharmacy in primary care/ADReGP
Protocol Version Number and Date	V2 08/01/2021
Methodology	Multiple-site parallel arm randomised controlled trial
Study Duration	Jan 2021 – Oct 2022 22 months
Study Centre	GP practices or community nurse-led clinics (Swansea Bay UHB, Hywel Dda UHB and Cardiff & Vale UHB)
Objectives	
• To establish the suitability/effectiveness of ADRe Profile for video call completion• To establish whether patients could complete parts of ADRe Profile themselves• To explore whether the ADRe Profile identifies health problems that could be attributable to polypharmacy and ameliorated (and record any changes to care, benefits or harms to the patients)• To explore whether routinely collected data could be used to populate the ADRe Profile
Number of Subjects/Patients	131 (35 – validity testing, 80 – patients, 16 – healthcare professionals)
Main Inclusion Criteria	Phase 1 
• Content validity index respondents: healthcare professionals (current or retired, working full-time or part-time, willing to

	
participate), service users (age > 64, willing to participate)
 
• Cognitive interview respondents: healthcare professionals (current or retired, working full-time or part-time, willing to participate), service users (age > 64, willing to participate)• Contrast group validity respondents: group A (people, age >64, no daily prescribed medicines - vitamin and nutritional supplements and moisturising skin preparations will not be counted as 'medicines', willing to participate), group B (as below)• Inter-rater reliability and feasibility participants: service users (age > 64 years, with a long-term condition, prescribed > 5 medications daily. (Vitamin and nutritional supplements and moisturising skin preparations will not be counted as 'medicines').), Willing and able to give informed, signed consent themselves, or where capacity is lacking in the opinion of their nurses, a consultee/representative accompanying the patient who is willing to give advice and assent to the service user participating and sign on their behalf. 
Phase 2
 
Service users:
 
• age > 64 years• with a long-term condition• prescribed > 5 medications daily. (Vitamin and nutritional supplements and moisturising skin preparations will not be counted as 'medicines').)• Willing and able to give informed, signed consent themselves, or where capacity is
--	--

	
lacking in the opinion of their nurses, a consultee/representative accompanying the patient who is willing to give advice and assent to the service user participating and sign on their behalf.
 
Nurses:
 
• Working in or alongside a general practice and expected to work there for the next 6 months 
Pharmacists and GP's:
 
• Aligned with the general practice, expected to stay in employment for the next 6 months 
Phase 3
 
No new participants, we shall approach people who took part in Phase 2.

Statistical Methodology and Analysis	
We are combining quantitative and qualitative methods of analysis to capitalize on the respective strengths of each of the approaches. The mixed methods will help to evaluate the intervention effect from a patient perspective, as well illustrate the conclusions derived from the quantitative data with stakeholder insight (Bharmal et al., 2018).
 
The overall design is sequential: QUAN Phase 1 informs QUAN + QUAL Phase 2, which informs convergent design Phase 3 (QUAN + QUAL), Itemised methods of analysis are described below:
 
Content Validity Index (CVI)
 
To be measured using Lynn's (1986) method:
 
Experts will rate each item using a four-point ordinal scale (1 = not relevant, 2 = somewhat relevant, 3 = quite relevant, and 4 = highly relevant)
 
Number of experts rating the item 3 or 4 will be divided by total number of experts
 
Result of 0.78 or above will be accepted as having met the validity threshold.
 
Scale content validity ratio will be calculated as a proportion of total items judged against content valid items.

	
Cognitive interviews Think aloud technique combined with participant confidence rating (the degree of confidence participant has in their answer) and observation (eg. To find out where people start reading, whether they look for instructions, whether they take longer to answer any particular questions)
 
Contrast group construct validity Numerical value will be added to ADRe responses (0 for 'no' answers and 1 for 'yes' or 'worse' answers. Numbers of problems will be compared for the group (n=20) without prescribed medicines and the group (n=20) that is prescribed > 4 medicines (these are participants of 1.2 ADRe testing).
 
Inter-rater Reliability (IRR) Cohen's Kappa will be calculated (Cohen, 1960) to compare patient and researcher completion.
 
Randomised Controlled Trial Data will be entered into excel via the electronic version of ADRe, imported into SPSS and described for the before and after ADRe administrations. Statistical analysis: differences between before and after the intervention will be calculated for: number and nature of problems addressed, prescription regimens, NHS use. The impact of GP practice, age, diagnoses, and medicines' use (numbers and types of medicines prescribed) will be described and accounted for. To explore the recorded changes and potential for further clinical gains, putative aetiologies of service users' signs and symptoms will be ascribed, using clinical information from medical and nursing records, including, but not restricted to, information on ADRe, and the list of medications prescribed (and over the counter) The ascription will be checked by supervisors using manufacturers' literature and formularies. Juxtaposition of ADRe and medication lists will generate suggestions for changes to improve the processes and possibly the

--	--

	
outcomes of care. The prevalence of problems on the before and after profiles will be compared with two by two contingency tables, using McNemar's test for related dichotomous variables (Altman 1991).
 
Survey
 
Data will be described using the Statistical Package for Social Sciences (SPSS) and later combined with the interview results.
 
Interviews and recorded ADRe consultations
 
All interviews (and relevant parts of ADRe consultations) will be transcribed verbatim by the researcher/professional transcriber and anonymised. Transcripts will be coded, categorised, analysed and interpreted alongside the data of all completed cases, to identify, analyse and report patterns within data (Braun and Clark, 2006). The transcripts will be analysed by the team using the constant comparative method which will provide a systematic, re-iterative way of comparing and contrasting emerging codes, categories and concepts and ensure that theoretical perspectives are embedded in the description of change. Two researchers ([name]) will ensure validity of the analysis and verify interpretation.
 
Disagreements will be resolved through discussion at team meetings. Diaries/logs will also be analysed in association with interview transcripts.
 
Triangulation
 
Survey and interview data will be integrated with the outcome measures documented on the ADRe Profile, taking a pragmatic perspective of complementary triangulation (Östlund et al., 2011). Resulting cross-cutting themes derived from the data should enhance understanding and validity, and contextualise the ADRe data (Foss & Ellefsen, 2002; Denzin, 2012).
 
Costs
 
Resource use, costs, and health economic outcome measures will be described using the Personal

--	---

SU Non CTIMP Healthcare Research Protocol

	
Social Services Research Unit (PSSRU) unit costs of health workers (www.pssru.ac.uk) and the National Tariff Payment Systems.
 
The regulatory and governance requirements will be met through gaining approval from the relevant review bodies to conduct the project.

--	--

Protocol Agreement Page

The clinical study as detailed within this research protocol

(Version 2, dated 8th January, 2021),

or any subsequent amendments will be conducted in accordance with the

- UK Policy Framework for Health and Social Care Research (2017)
- Medicines for Human Use (Clinical Trials) Regulations (2004)
- Medical Devices Regulations (EU MDR/IVDR 2017)

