1.3 Clinical Data

Medication monitoring and monitoring patients for potential adverse drug reactions has been described as an 'orphan task' in the past due to its position on the interprofessional boundary between pharmacy, medicine and nursing and the subsequent deficiency in ownership (Jordan, 2002, Jordan et al., 2016). Recent studies confirm the lack of clarity of the nurses' roles in medication management (De Baetselier et al., 2019) and effective teamwork has been affirmed as a facilitator of safe management of polypharmacy (WHO, 2019), and medication management overall (WHO, 2017). ADRe Profile is an instrument that involves nurses, pharmacists, prescribers and patients in monitoring for adverse drug reactions to medicines. Nurses and patients identify the problems and may solve some of them, pharmacists review the medicines and prescribers may be provided with recommendations to consider adjustment of the prescriptions.

To date, two randomised controlled trials and five observational/before and after studies have investigated the clinical impact of the ADRe Profile. In total, 168 study participants had the ADRe Profile implemented. Majority of the participants were prescribed mental health medicines (antipsychotics, antidepressants or anti-epileptics), one study included patients with respiratory diseases, taking bronchodilators, corticosteroids or leukotriene receptor antagonists. The setting was mostly in the community, with 3 nursing homes, 3 community mental health settings and one outpatient respiratory clinic.

In two of the community mental health settings, the mean number of problems actioned increased from 0.35 with no ADRe Profile to 3 with ADRe Profile (Jordan et al., 2002; Jordan, 2002). Little change in the number of problems actioned was noted in the comparator groups. The mean number of problems detected increased from 2 without the Profile to 9 with the Profile in one of the studies (Jordan, 2002), no information was offered in the other study. Most actions taken were to alleviate physical health problems.

Another study from an acute mental health service setting identified and addressed health problems for all participants (the mean increase of actions taken was 11.9, SD = 4.7, range 2-20) (Jones et al., 2016). Some of the problems identified were orthostatic hypotension, hypertension, constipation or inadequate diet, two of the

SU Non CTIMP Healthcare Research Protocol

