1.4 Rationale and Risks/Benefits

This study concerns optimisation of medicines monitoring and multidisciplinary team involvement in medicines management and optimisation. Similar projects have not encountered major ethical, legal or management issues, and we do not envisage any here. The Adverse Drug Reaction (ADRe) Profiles for nurse-led medicines monitoring have benefitted patients in all previous trials and observation studies and no harms have been reported. In this study, the instrument will be adapted for use in general practices and the feasibility of its adoption will be explored by the researchers. The ADRe Profile has recently been endorsed by the Royal Pharmaceutical Society and All Wales Medicines Strategy Group (AWMSG). Embedding the ADRe Profiles thus represents an addition of an established

SU Non CTIMP Healthcare Research Protocol

instrument to the nursing documentation and the risk of physical and emotional harm from the instrument is predicted to be minimal, and no more than in routine clinical interviews. Vital signs will be recorded. Results of ECGs, lung function tests and laboratory results will be noted as 'present / absent': these tests are not part of the study.

Risks and burdens according to study participants:

Content validity index and construct validity respondents: we foresee no potential risk of physical or emotional harm to competent adult respondents completing an electronic document from their own computers in their own time.

Cognitive interview participants: we foresee no potential risk of physical or emotional harm to competent adult respondents reading through a draft instrument with a trained research fellow in their own time. Respondents will be asked questions on validity and interpretation of the instrument. They will not be asked any questions about themselves or expected to divulge any personal information. No identifiable data will be collected.

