2.1 Trial Objectives

Primary Objectives

- To establish the suitability/effectiveness of ADRe Profile for video call completion
- To establish whether patients could complete parts of ADRe Profile themselves
- To explore whether the ADRe Profile identifies health problems that could be attributable to polypharmacy and ameliorated (and record any changes to care, benefits or harms to the patients)
- To explore whether routinely collected data could be used to populate the ADRe Profile

Secondary Objective

- To establish the validity and reliability of the ADRe Profile
- To explore the feasibility of linking the electronic ADRe Profile to GP electronic records
- To report how ADRe Profile contributes to efficient collaboration of the multiprofessional team (nurses, care assistants, pharmacists, GP's) in monitoring the effects of patients' medications
- To report how ADRe contributes to patient-centered care
- To estimate costs associated with ADRe implementation

Primary Endpoint

Phase 1

- Content validity index (overall assessment of validity of the instrument)
- Construct validity (overall assessment of validity of the instrument)
- Cognitive interviews: Enhanced understanding how participants answer the ADRe questions.
- Inter-rater reliability of patient versus nurse-researcher completed ADRe Profile (Cohen's Kappa) - (To determine how much of the potential variability of the records is due to errors in measurement, to estimate a degree to which service users accurately evaluate their symptoms when compared with a nurse researcher, to determine suitability of ADRe for patient self-completion. Cohen's Kappa will be calculated.) [Time Frame: 4 months from the start of the study]
- Level of completion of all items in the video call-completed ADRe Profile. (Comparison of completeness of the ADRe Profile completed through a video

call with ADRe Profiles previously completed in person, suitability of ADRe Profile for video call completion.) [Time Frame: 4 months from the start of the study]

- Calculated percentage and described nature of items on the ADRe Profile that can be populated from accessing the nursing and medical notes. (Establishing the overlap of information - the number and nature of the ADRe items that have previously been collected and recorded in the patients' nursing and medical notes.) [Time Frame: 16 months from the start of the study]

Phase 2

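### The content validity index scores only items already on the ADRe Profile, so it cannot fall when a needed problem is missing and should not be labelled an overall assessment of validity

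*Combined protocol and SAP*

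**What the plan says.** The synopsis and section 7.5 describe the same procedure. Raters score each item for relevance: "Experts will rate each item using a four-point ordinal scale (1 = not relevant, 2 = somewhat relevant", continuing to 4 for highly relevant. Then "Number of experts rating the item 3 or 4 will be divided by total number of experts", and "Result of 0.78 or above will be accepted as having met the validity threshold". For the whole instrument, "Scale content validity ratio will be calculated as a proportion of total items judged against content valid items". Section 3.1 sets the panel at 10: two each of GPs, pharmacists, nurses, care assistants and patients.

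Section 2.1 lists the result among the Phase 1 primary endpoints as "Content validity index (overall assessment of validity of the instrument"; construct validity carries the same label. A further Phase 1 endpoint describes the "items on the ADRe Profile that can be populated from accessing the nursing and medical notes".

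On the background, section 1.3 reports of the earlier studies that "Majority of the participants were prescribed mental health medicines (antipsychotics, antidepressants or anti-epileptics", and section 1.4 says that "the instrument will be adapted for use in general practices".

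**The concern.** Content validity has two sides: whether the items present belong, and whether the set of items is complete. The index as described addresses only the first. It can flag a surplus item but cannot register an absent one.

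Completeness is a fair question here because the instrument is moving to a new setting. Section 1.2 expects cardiovascular, respiratory, endocrine, neurological, mental health and musculoskeletal conditions, whereas most earlier participants took mental health medicines. Phase 1 feeds Phase 2 (section 7.5), and its results can stop the study (End of Study Definition). One primary objective is to explore whether the Profile identifies problems that polypharmacy could explain. If a high index were read as showing that the content is complete, an omission could carry into the trial without any planned measure having tested for it.

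**Working it through.** **Inputs from the documents.** 10 raters (section 3.1); an item passes at 0.78 or above; the scale ratio uses items judged and items found valid (synopsis and section 7.5). The documents give no item count, so K (items judged) and m (needed problems with no item) are assumed below.

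**1. The plan's own figure.** Item index = (ratings of 3 or 4)/10. Since 7/10 = 0.70 fails and 8/10 = 0.80 passes, the 0.78 threshold means at least 8 of 10 raters. It is a chosen cut-off, so there is no derivation to reproduce.

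**2. Does m enter the index?** Scale ratio = valid items/items judged = V/K. Coverage of needed problems, if every judged item is needed, is K/(K + m). With all items passing, V = K:

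| K (assumed) | m (assumed) | Scale ratio | Coverage |
|---|---|---|---|
| 40 | 0 | 40/40 = 1.00 | 40/40 = 100% |
| 40 | 10 | 40/40 = 1.00 | 40/50 = 80% |
| 40 | 20 | 40/40 = 1.00 | 40/60 = 67% |
| 60 | 5 | 60/60 = 1.00 | 60/65 = 92% |

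The wording of the scale ratio can also be read as K/V. That gives 1.00 in every row too. On either reading m appears in no term.

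**3. Do the other Phase 1 measures see m?**
- Construct validity counts 0/1 answers to the same items in two groups of 20.
- Cohen's kappa compares patient and researcher answers to the same items.
- Video-call completeness is the extent to which existing items are filled in.
- The notes endpoint goes from Profile to notes, asking which items can be found there. It does not ask which noted problems have no item.
- The five cognitive interviews use think-aloud, confidence ratings and observation. Section 1.4 adds questions on validity and interpretation, but no completeness question and no rule for adding items.

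**4. What could a search for omissions find?** If each rater independently named a given omission with probability q, the panel would find it with probability 1 − (1 − q)^10. At q = 0.10 this is 1 − 0.90^10 = 65%; at q = 0.20 it is 1 − 0.80^10 = 89%. Both q and independence are assumptions.

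Only the 20 Phase 1 patients' notes are read before the trial. A problem recorded in a share p of patients appears at least once with probability 1 − (1 − p)^20. At an assumed p = 5% this is 1 − 0.95^20 = 64%; at 2% it is 1 − 0.98^20 = 33%.

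**The case against.** The best defence is that an index of relevance measures relevance, and that the plan does not rest validity on it alone. Construct validity has the same label, and cognitive interviews are a separate endpoint. Several routes could bring an omission to light: the interview questions on validity, the Phase 2 clinical endpoint drawn from notes as well as the Profile (section 2.1), the aetiology review using records beyond the Profile (section 7.5), and the pharmacist's review of the Profile with the medicines list (section 6.8). The plan also cites a published method that may include an omission step, and neither the rating form nor the Profile is among the documents. The Profile might have an open field for other problems.

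Much of this stands. It means that omissions would not necessarily go unnoticed. But each route is informal, with no stated completeness criterion or rule for adding items, and those in Phase 2 operate once the Profile is already in use.

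A reader might go further and infer that the Profile does omit medicine harms relevant to general practice. The documents do not support that. Section 1.3 describes mainly physical problems being acted on, across care homes, mental health services and a respiratory clinic. Sections 3.1 and 7.4 cite earlier use of ADRe Profiles for polypharmacy, in which 17 of 19 participants improved.

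**Conclusion.** The point holds in a limited form. As described, the index cannot respond to missing content, and its label in section 2.1 claims more than it measures. This follows from the formulas and needs no assumed figure; the coverage percentages depend on assumed K and m and only illustrate the size of the gap. No harm is shown to be missing, and the cited method could not be consulted.

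It might also be inferred that reading the notes of all 80 patients would repair the Profile before the trial. It would not: 60 of them are trial patients, whose notes are read once Phase 2 is under way. The relevant figures are the 64% and 33% for 20 patients. This is a cheap improvement to Phase 1, not a flaw in the trial's main comparison.

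**What to change.** 1. Add one open question to the content validity form, asking the 10 raters to list any medicine-related problem in this population that has no item.
2. Review the answers before the Phase 2 version of the Profile is fixed, with a stated rule for adding an item and having it rated.
3. In section 2.1, describe the index as item relevance, and report the named omissions beside it. Clarify at the same time that the scale ratio is valid items divided by items judged.
4. Optionally, while notes are already being read, list noted problems that match no item and report them descriptively. This list is secondary: it cannot capture problems absent from the notes, which are the ones the Profile is meant to bring out.

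No new participants or visits are needed. The costs are some coding, clinical judgement on which listed problems are medicine-related, and possibly a slightly longer Profile.
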